## PROTOCOL SUMMARY

Study Title	Arch-Clamping Technique under Mild Hypothermia in Treating with Acute Type A Aortic Dissection: Study Protocol for a Multicenter, Three-arm, Open-label, Randomized, Parallel-controlled Trial
Study Objectives	
(1) To evaluate the validity and safety of arch-clamping technique under mild hypothermia for acute type A aortic dissection (ATAAD) using Sun's procedure with bilateral anterograde cerebral perfusion (bACP) as the comparator.
 
(2) To evaluate the validity and safety of arch-clamping technique under mild hypothermia for ATAAD using arch-clamping technique under moderate hypothermia as the comparator.

Study Design	Multicenter, Three-arm, Open-label, Parallel-controlled, Randomized, Superiority Study
Sample Size	This study plans to include 306 participants, divided into three groups of 102 participants each in a 1:1:1 ratio.
Inclusion Criteria	
(1) Computed tomography angiography (CTA) confirmed as ATAAD according to the 2022 ACC/AHA Guideline for the Diagnosis and Management of Aortic Disease;
 
(2) Adult patients (18-70 years) weighing 50-120 kg;
 
(3) Time interval between the onset of symptoms and operation is less than 14 days;
 
(4) Indications for total aortic arch replacement are available;
 
(5) Signed informed consent and availability for follow-up.

Exclusion Criteria	
(1) History of chronic renal failure, hepatocirrhosis, and hepatic insufficiency;
 
(2) Severe gastrointestinal complications of non-aortic dissection, such as mesenteric ischemia, gastrointestinal bleeding, hepatopancreaticobiliary dysfunction, and intestinal obstruction;

	
(3) History of severe cerebral infarction (with cerebral infarction sequels);
 
(4) Preoperative intubation or unconsciousness;
 
(5) Inflammatory aortic diseases, such as Takayasu arteritis and Behçet's disease etc;
 
(6) History of infectious aortic diseases;
 
(7) History of cardiac and aortic surgery;
 
(8) History of malignancy or previous radiotherapy;
 
(9) Pregnant or feeding women, or anyone planning to reproduce during the test period;
 
(10) Without informed consent signature;
 
(11) Participating in any other clinical trial;
 
(12) Having other causes not eligible for operation.

Study Period	June 2025 to June 2027

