## Statistical Considerations

### Sample Size

#### Estimation of Total Sample Size

Sample size estimation is performed using PASS 2021 software.

This study adopts a superiority design and a fixed sequence testing strategy. The primary outcome is the incidence of composite events, which is a low-benefit endpoint. The hypotheses are as follows:

- ① Experimental Group 1 is superior to the control group.
- ② Experimental Group 1 is non-inferior to Experimental Group.

The order of hypothesis testing is ①→②. According to the *Guideline on Multiplicity in Clinical Drug Trials*, this strategy will not inflate the overall Type I error rate (FWER), and no adjustment for multiplicity is required.

Based on previous research, the incidence of composite events with mild hypothermic aortic arch clamping combined with bilateral cerebral perfusion is approximately 13.64%, with moderate hypothermic arch clamping combined with unilateral cerebral perfusion is approximately 22.67%, and with the traditional Sun's procedure is approximately 29.63%.

For hypothesis ①, assuming the composite event rate is 13% in Experimental Group 1 and 30% in the control group, with a superiority margin set at 0, a one-sided significance level of 0.025, a power of 80%, and an allocation ratio of 1:1, at least 91 subjects are required in each group.

For hypothesis ②, assuming the composite event rate is 25% in Experimental Group 2 with a non-inferiority margin of 5%, at a one-sided significance level of 0.025, a power of 80%, and an allocation ratio of 1:1, at least 84 subjects are required

in each group.

In summary, taking the maximum required sample size above and allocating subjects in a 1:1:1 ratio among the three groups, and accounting for a 10% dropout rate, a total of 306 subjects will be enrolled in this study, with 102 subjects in each group.

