## **Primary Endpoint Analysis**

Analysis of the primary endpoint will be based on both FAS and PPS.

The primary efficacy endpoint of this study is the incidence of composite events, and a superiority test will be used.

Hypotheses for test ① are as follows:

Null hypothesis:  $T_1 - C \geq 0$

Alternative hypothesis:  $T_1 - C < 0$

Where  $T_1$  is the incidence of composite events in Experimental Group 1, and  $C$  is that in the control group. The difference in composite event rates between the two groups and the 95% confidence interval will be calculated. If the upper limit of the 95% confidence interval is less than 0, superiority is established.

Hypotheses for test ② are as follows:

Null hypothesis:  $T_1 - T_2 \geq 0.05$

Alternative hypothesis:  $T_1 - T_2 < 0.05$

Where  $T_1$  is the incidence of composite events in Experimental Group 1, and  $T_2$  is the incidence in Experimental Group 2. The difference and 95% confidence interval

between the two groups will be calculated. If the upper limit of the 95% confidence interval is less than 0.05, non-inferiority is established.

Testing will follow the fixed sequence of ①→②; if the previous hypothesis test is met, the subsequent comparison will be performed; otherwise, further comparison will be stopped.

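### Group 1 versus Group 2 is tested only for non-inferiority; a third, superiority step on the interval already planned would cost no alpha and allow a pre-declared claim on temperature

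*Combined protocol and SAP*

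**What the plan says.** The Protocol Summary gives the design as "Multicenter, Three-arm, Open-label, Parallel-controlled, Randomized, Superiority Study", with nothing to limit the last term. Under Estimation of Total Sample Size the plan says "This study adopts a superiority design and a fixed sequence testing strategy", and under Primary Endpoint Analysis "The primary efficacy endpoint of this study is the incidence of composite events, and a superiority test will be used". Both of these sections then write out two hypotheses, and the second is non-inferiority:

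- Test ①, Group 1 versus control: superiority if the upper 95% limit of T1-C is below 0.
- Test ②, Group 1 versus Group 2: "If the upper limit of the 95% confidence interval is less than 0.05, non-inferiority is established".

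The sequence closes after the second test: "The order of hypothesis testing is ①→②". Neither section says what may be concluded, or what is ruled out, if the T1-T2 interval lies wholly below 0.

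The second objective under Study Objectives asks only for an evaluation against moderate hypothermia. It neither promises nor excludes a superiority claim. On analysis sets the plan says "Analysis of the primary endpoint will be based on both FAS and PPS", without saying which set decides. No confidence interval method is named.

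**The concern.** Group 1 versus Group 2 is the only contrast that isolates temperature, since the Interventions section gives both arms the same clamping technique with bilateral cerebral perfusion. The Rationale for Study Design names the move from moderate to mild temperature as one of two optimizations behind the three-arm design. The Background reports lower mortality and morbidity with mild hypothermia. The sample size for test ② rests on a 12-point benefit (13% versus 25%).

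The sponsor therefore expects benefit on this contrast, but the strongest conclusion declared in advance is that Group 1 is less than 5 points worse. If the data show benefit, the interval will be published, but reading it as superiority will be a choice made after the result is known, in a trial without blinding. What is at stake is the status of that claim and the room left for selective emphasis.

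**Working it through.** **Inputs.** All are from Estimation of Total Sample Size: 13% (Group 1), 25% (Group 2), 30% (control); margin 5 points; one-sided 0.025; power 80%; 91 and 84 per group; 10% dropout; 102 per group. The prior rates given there are 13.64%, 22.67% and 29.63%. The 13% for Group 1 is stated for test ① and carried over to test ②.

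**1. The plan's own figures.** With pooled variance under the null,

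n = [1.96·√(2p̄(1-p̄)) + 0.8416·√(p1(1-p1)+p2(1-p2))]² / distance².

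- Test ①: p̄ = 0.215, distance 0.17, n = 90.5, so 91 (stated 91).
- Test ②: p̄ = 0.19, distance 0.05 + 0.12 = 0.17, n = 83.005, so 84 (stated 84).
- Dropout: 91/0.90 = 101.1, so 102 per group and 306 in total (as stated).

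The stated sizes reproduce.

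**2. Chance that the T1-T2 upper limit falls below 0.** Normal approximation: Φ(|difference|/SE - 1.96), with SE = √[(p1(1-p1)+p2(1-p2))/n].

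- 13% v 25%, n = 91: SE = √(0.3006/91) = 0.0575; 0.12/0.0575 - 1.96 = 0.128; Φ = 0.551.
- The same rates, n = 102: SE = 0.0543; 0.251; Φ = 0.599.
- 13.64% v 22.67%: 0.356 at n = 91 and 0.391 at n = 102.

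Exact binomial enumeration:

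| Rates, Group 1 v Group 2 | n per arm | Newcombe | Wald |
|---|---|---|---|
| 13% v 25% | 91 | 0.544 | 0.560 |
| 13% v 25% | 102 | 0.589 | 0.604 |
| 13.64% v 22.67% | 91 | 0.350 | 0.365 |
| 13.64% v 22.67% | 102 | 0.381 | 0.396 |

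**3. Chance of meeting ①, ② and the added step ③ together** (shared Group 1 count; Newcombe to Wald).

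- 13/25/30%: 49.5-51.2% at 91 per arm, 54.7-56.3% at 102.
- Prior rates: 31.8-33.4% at 91 per arm, 35.4-36.9% at 102.

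**4. Error of the added step.** A T1-T2 upper limit below 0 is also below 0.05, so ③ is nested in ② and uses the same interval. With equal true rates between 13% and 30%, at 91 and 102 per arm, the exact one-sided error of ③ taken alone is 2.35-2.51% (Newcombe) or 2.53-2.70% (Wald). Requiring ① first cannot raise it.

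**5. Worked counts at 91 per arm.**

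- 12 v 23 events (the planning rates, rounded): difference -11/91 = -12.1 points. The Wilson limits are 7.7-21.6% for 12/91 and 17.5-35.1% for 23/91. Newcombe upper limit = -0.1209 + √[(0.2165-0.1319)² + (0.2527-0.1747)²] = -0.1209 + 0.1151 = -0.0058. The interval is -23.3 to -0.6, so ② and ③ are met.
- 12 v 21 events (the prior rates, rounded): -9.9 points, interval -21.0 to +1.4. Only ② is met.
- With 23 events in Group 2, ③ is met at 12 or fewer Group 1 events and ② alone at 13-16, by either method.

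**6. Size for 80% power of ③.** The formula in step 1 with distance 0.12 gives 166.6, so 167 per arm. At the prior rates (distance 0.0903) it gives 284.9, so 285.

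**The case against.** The strongest reply is that nothing is wrong. Non-inferiority against Group 2 is written out in both statistical sections, the T1-T2 difference and interval are already planned, and a closed two-step sequence can fairly be read as saying that anything beyond non-inferiority is descriptive. This largely stands. A reader might infer that three superiority labels contradict the test, but the two statistical sections qualify their own wording by stating test ②; only the Protocol Summary line stands alone. A reader might also infer that judging the interval against 0 would inflate the type I error. It would not, because the hypotheses are nested.

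A second reply is that ③ is a design preference at 35-60% power. It is indeed optional. The case for it is that it costs nothing and answers a question that the three-arm design was built to ask.

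Third, the unnamed interval method matters little in practice. Counts of 11 v 21 out of 91 give an upper limit of +0.15 points (Newcombe) or -0.04 (Wald), but the two methods disagree about 0 in only about 1.5-1.6% of trials at either pair of rates. This stands. The method and the deciding set are worth fixing because ① and ② need them as much as ③ does.

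Two limits remain. The time horizon of the composite is also unsettled: death is defined to 30 days or discharge but observed to 12 months, and the flowchart collects all components to 12 months. That is a separate point. Also, the Progress Schedule places enrolment from June 2025 to May 2026, and a change made during open-label enrolment protects less than one made at the start.

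**Conclusion.** The point holds as an improvement that costs no alpha, patients or data. It is not a defect in the test chosen or in the sample size, which reproduces. On the sponsor's planning rates, an interval wholly below 0 is slightly more likely than not (54-60%), and the plan declares no conclusion for it beyond non-inferiority. At the prior rates the chance is 35-40%. It may be lower still, because the 22.67% comes from unilateral perfusion ("with moderate hypothermic arch clamping combined with unilateral cerebral perfusion is approximately 22.67" per cent), whereas Group 2 receives bilateral perfusion.

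These figures assume independent binomial counts, 91-102 analysed patients per arm and a 95% Newcombe or Wald interval. The gain is a confirmatory claim declared in advance and less room for selective emphasis; error control is unchanged. The documents do not support reading success on ② as superiority over moderate hypothermia, nor treating ③ as a powered objective.

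**What to change.** 1. In both Estimation of Total Sample Size and Primary Endpoint Analysis, extend the sequence to ① superiority over control, ② non-inferiority to Group 2, ③ superiority over Group 2 (null T1-T2 ≥ 0, alternative T1-T2 < 0). Step ③ is tested only if ① and ② are met, and is met if the upper limit of the same T1-T2 95% interval is below 0.
2. State that ③ is not powered: about 54-60% at 13% v 25% and 35-40% at 13.64% v 22.67%, noting the unilateral-perfusion source of 22.67%. State that ② without ③ supports only non-inferiority.
3. Name one interval method for all three steps, for example Newcombe, and name the deciding analysis set for each of ①, ② and ③, so that each contrast has one interval.
4. Change the Protocol Summary label to superiority versus control; non-inferiority then superiority versus Group 2.
5. Make the amendment before any comparison of outcomes by arm.

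If the sponsor declines ③, state that only non-inferiority will be claimed against Group 2, and correct the Protocol Summary label accordingly.

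The cost is one amendment, with the ethics approval required under Ethical Considerations and the retraining required under Investigator Training and Retraining at the 7 hospitals.

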## **Secondary Endpoint Analysis**

Analysis of secondary endpoints will be conducted based on both FAS and PPS.

Statistical analysis methods will follow the general principles described above.

## **Handling of Missing and Abnormal Values**

(1) Handling of missing data: No imputation of missing data will be conducted; analysis will be based on the data actually obtained.

(2) Handling of erroneous data: Investigators shall make written corrections to erroneous data. The database can only be locked after all errors have been corrected.

(3) Handling of unreasonable data: Investigators shall make written adjustments to unreasonable data. The database can only be locked after all unreasonable data entries have been addressed.

## **Data Management**

### **Selection of EDC System**

An EDC (Electronic Data Capture) system will be used for data collection.

### **Case Report Forms**

An electronic Case Report Form (eCRF) will be used for clinical trial data collection. The eCRF will be designed based on the study protocol and paper CRF to define data collection tables, the study workflow, names of data forms, and collected data items. A corresponding data collection manual will be developed, reviewed and approved by the study team before finalization. All information entered in the eCRF

must be sourced from the subject's original records.

## **Database Creation and Data Collection**

The data manager will establish the eCRF according to the study protocol and paper CRF and will be responsible for its testing. The testing includes page design, visit period settings, order of forms and data points for each visit, and the accuracy of user-specific access permissions.

Each user will be assigned a unique username and password. Designated personnel at the study centers will enter original data into the eCRF via a secure network. Investigators are required to collect subject data in accordance with the study protocol and complete the eCRF accurately, promptly, completely, and in compliance with the data entry guidelines. The eCRF does not serve as a source document; it will generate relevant prompts and allow site personnel to modify the entries. Prior to database lock, investigators will confirm the accuracy of data entries via electronic signature.

## **Database Lock**

The database will be locked by the data manager after joint signature by the principal investigator and the data manager on the database lock record.

## **Preservation and Handover of Data Management Documentation**

Data management personnel shall retain relevant documentation as required and transfer the locked database and associated materials to the statistical analysis team for statistical analysis.

## **Risk-Benefit Analysis**

### **Potential Risks**

This project is an interventional study. According to current experience and published literature, both aortic arch clamping with bilateral cerebral perfusion (Experimental Groups 1 and 2) and conventional TAR + FET surgery (Control Group)

can safely and effectively treat ATAAD. None of these surgical techniques are expected to increase operative risk. However, it should be noted that ATAAD itself carries risks such as preoperative pericardial tamponade and vascular rupture leading to patient death, as well as loss of surgical indications due to poor organ perfusion. In addition, there are risks of postoperative death and related complications resulting from the surgical intervention itself.

## **Potential Benefits**

The conventional TAR+FET procedure has well-established surgical efficacy. Aortic arch clamping combined with bilateral cerebral perfusion may further reduce circulatory arrest time and overall operative time, decrease in-hospital mortality and related complications, and potentially improve long-term outcomes. Considering the principles of randomized controlled study design, all treatment strategies in this trial aim to maximize the chance of saving patients' lives through surgical intervention.

## **Quality Control in Clinical Trials**

### **Quality Control Measures**

All investigators must adhere to standard operating procedures to ensure the implementation of quality control and quality assurance systems in the clinical trial. All observations and findings in the clinical trial should be verified to ensure data reliability, and all conclusions must be based on original data. Quality control must be implemented at each stage of data processing to ensure that all data are reliable and correctly handled.

## **Investigator Training**

To ensure the quality of the clinical trial, all investigators must undergo training prior to trial initiation. Training includes, but is not limited to, the study protocol, surgical procedures, and the recording and reporting of adverse events. Ongoing training should be provided as needed during the course of the trial. Whenever there

are significant updates to the protocol or relevant documents, retraining of the investigator team is required. Investigators who join the trial after the initial investigator meeting must receive comprehensive training before participating in any trial-related activities.

## **Enhancing Subject Compliance**

Investigators should ensure that informed consent is properly obtained so that subjects fully understand the trial requirements and cooperate with the study.

Investigators should also instruct subjects to promptly report their health status after discharge to monitor the occurrence of adverse events and complications. During follow-up visits, subjects must bring all medications they are currently taking for review of concomitant medications, which should be recorded in the CRF.

## **Ethical Considerations and Informed Consent in Clinical Trials**

### **Ethical Considerations**

Clinical trials must be conducted in accordance with the *Declaration of Helsinki* and relevant national regulations and guidelines for clinical trials.

Prior to the trial, the investigator must submit the study protocol, informed consent form, and other relevant documents to the medical ethics committee of the hospital responsible for the clinical trial. The clinical trial may only commence after approval by the ethics committee. Any amendments to the protocol must also be approved by the ethics committee before implementation. Serious adverse events occurring during the clinical trial must be promptly reported in writing to the ethics committee.

### **Informed Consent Process**

Before enrolling each subject, the investigator is responsible for providing a complete and comprehensive written explanation of the study's purpose, procedures, and potential risks. Subjects must be informed of their right to withdraw from the trial

at any time and assured that their personal information will remain confidential. Each subject must receive a written informed consent form before enrollment, and the investigator must ensure that informed consent is obtained prior to participation. The signed informed consent form should be retained as part of the clinical trial documentation.

If a subject is unable to read, an impartial witness must be present during the informed consent process. After a detailed explanation of the informed consent form, the impartial witness should confirm that the written and oral information are consistent. Upon the subject's oral consent, the impartial witness must sign and date the informed consent form on the same day as the investigator.

## **Adverse Event Reporting Requirements**

### **Adverse Events**

#### **Definition of Adverse Events**

An adverse event (AE) refers to any unfavorable medical occurrence that arises during the course of a clinical trial.

#### **Severity of Adverse Events**

The severity of adverse events will be graded according to the Common Terminology Criteria for Adverse Events (CTCAE), version 5.0. The grading criteria for adverse events are shown in the table below.

Adverse Event Evaluation Criteria	
Severity Grade	Criteria 
Grade 1	Mild: asymptomatic or mild symptoms; only clinical or diagnostic observations; no intervention required.
Grade 2	Moderate: minimal, local or noninvasive intervention indicated; Instrumental activities of daily living (IADL)  are limited.
Grade 3	Severe or medically significant but not immediately life-threatening; hospitalization or prolongation of hospitalization indicated; disabling; self-care activities of daily living (ADL)  are limited.
Grade 4	Life-threatening; urgent intervention indicated.

---

Grade 5      Death related to adverse event.

---

Note:

 In the criteria, “ ; ” denotes “or”.

 Instrumental activities of daily living include preparing meals, shopping for groceries or clothes, using the telephone, managing finances, etc.

 Self-care activities of daily living include bathing, dressing, eating, using the toilet, taking medications, and remaining in bed as needed.

## Management of Adverse Events

### General Principles

Once an adverse event occurs, the investigator must ensure that the subject receives adequate and timely treatment and management. All adverse events/serious adverse events must be followed up until one of the following occurs:

- ① The event resolves.
- ② The event stabilizes.
- ③ The event returns to baseline, if a baseline value is acceptable.
- ④ No further information can be obtained (e.g., the subject or caregiver refuses to provide further information, or the subject is lost to follow-up despite documented efforts).

### Special Notes

(1) Vital Sign Changes: During surgery, extracorporeal circulation replaces the subject’s own circulatory system, and postoperative recovery of circulatory function takes time. Additionally, postoperative psychological stress, wound pain, and nursing interventions may cause fluctuations in vital signs or require vasoactive or inotropic support. A postoperative mean arterial pressure of 60-90 mmHg is considered reasonable; blood pressure or other vital sign fluctuations outside this range should be assessed by the investigator for clinical significance. If considered potentially life-threatening or requiring urgent intervention, these should be reported as AEs. Non-life-threatening fluctuations or abnormalities in vital signs are not to be recorded as AEs.

(2) Resorptive Fever: Postoperative fever is common due to absorption of sterile

necrotic material. Investigators should evaluate postoperative fever based on symptoms, signs, and laboratory findings. Simple postoperative resorptive fever should not be reported as an AE; if fever is judged to be due to infection or other causes, it should be reported as an AE.

(3) Laboratory Abnormalities: Due to stress response, intraoperative ischemia-reperfusion injury, and anticoagulation during extracorporeal circulation, some laboratory parameters (e.g., blood count, biochemistry, coagulation, blood gases) may be abnormal postoperatively. Investigators should interpret isolated laboratory abnormalities in the context of the subject's symptoms, signs, imaging, and other laboratory findings. Transient, mild abnormalities do not require AE reporting. Progressive or severe abnormalities, or those requiring special intervention, should be reported as AEs.

(4) Anemia: Hemodilution and blood loss during extracorporeal circulation frequently necessitate perioperative transfusion. For perioperative anemia (e.g., decreased hemoglobin or hematocrit), investigators should make a comprehensive assessment based on clinical findings and imaging. Anemia that is corrected by routine transfusion does not require AE reporting; however, ongoing bleeding or transfusion-refractory anemia should be reported as an AE.

(5) Wound Pain: Significant wound pain is common after major cardiac surgery and is generally not reported as an AE. If the pain is persistent, severe, or judged by the investigator to have a serious impact on prognosis, it should be reported as an AE.

(6) Postoperative Fluid Collection: Inflammatory exudate may cause mild postoperative fluid collection at the surgical site, which is usually self-limiting. Investigators should comprehensively assess symptoms, signs, and laboratory data to exclude active bleeding or infection. Fluid collections that are non-progressive and do not require drainage or special intervention are not reported as AEs.

(7) Neuropsychiatric Complications: Postoperative delirium may occur due to reduced cerebral perfusion during extracorporeal circulation and the effects of anesthesia. Psychological stress and wound pain may also result in anxiety,

depression, or sleep disorders. If these symptoms do not require consultation or treatment by a psychiatrist or neurologist, they are not reported as AEs.

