## **Serious Adverse Events**

A serious adverse event (SAE) is defined as any event occurring during the clinical trial that results in death or significant deterioration in health, including life-threatening illness or injury, permanent impairment of body structure or function, hospitalization or prolonged hospitalization, or the need for medical intervention to prevent permanent impairment. Events resulting in fetal distress, fetal death, congenital anomaly, or birth defect are also included.

The following hospitalizations are not to be recorded or reported as SAEs: hospitalizations for diagnosis or elective treatment of preexisting conditions, hospitalizations for insurance reimbursement, planned hospitalizations or elective surgeries not related to an adverse event, or admissions for comprehensive physical examination.

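### The exemptions for delirium and vital signs conflict with the AE and SAE definitions, and recording of delirium turns on which specialist is needed

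*Combined protocol and SAP*

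**What the plan says.** Four parts of the adverse-event chapter bear on this point.

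- **Definition of Adverse Events** sets a wide capture rule: "An adverse event (AE) refers to any unfavorable medical occurrence that arises during the course of a clinical trial".
- **Severity of Adverse Events** applies CTCAE version 5.0. Grade 3 reads in part: "Severe or medically significant but not immediately life-threatening; hospitalization or prolongation of hospitalization indicated".
- **Special Notes** narrows what is captured. Item (1), on vital signs, keeps events judged to threaten life or to need urgent treatment, then closes: "Non-life-threatening fluctuations or abnormalities in vital signs are not to be recorded as AEs". Item (7) names delirium, anxiety, depression and sleep disorders and closes: "If these symptoms do not require consultation or treatment by a psychiatrist or neurologist, they are not reported as AEs". It traces delirium both to lower brain perfusion on bypass and to anaesthesia.
- **Serious Adverse Events** covers any event with one of the listed consequences, among them "hospitalization or prolonged hospitalization, or the need for medical intervention to prevent permanent impairment". It has its own list of exclusions, all of them types of hospital admission, and does not refer to the Special Notes. Reporting Procedures requires an SAE to be reported within 24 hours of awareness.

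Rationale for Study Design states that researchers and participants cannot be blinded and that randomization is done at each centre. Group 1 is operated on under mild hypothermia and both comparators under moderate hypothermia.

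**The concern.** The same patient can fall under two opposite instructions. Delirium managed by the ICU or surgical team that prolongs hospitalization meets the SAE definition and is due within 24 hours, yet item (7) says it is not an AE. A non-life-threatening vital-sign abnormality that prolongs hospitalization meets the SAE definition, yet item (1) says it is not recorded. Each of the 7 hospitals has to decide for itself which text governs.

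Item (7) also uses an unusual threshold. Items (2) to (6) bring events back into reporting by cause, severity, course or need for intervention. Item (7) looks only at which specialist is required, so duration, severity and seriousness play no part.

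Both study objectives name safety alongside validity, and the experimental arm is the warmer one. Delirium that is not a stroke is a cerebral event that a reader of the results would want counted in the same way in every arm.

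**Working it through.** The plan states no figure on this point, so the check is a comparison of texts, followed by an illustration on stated assumptions.

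**1. The rules applied to five situations**

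| Situation | AE definition | Special Notes | SAE definition |
|---|---|---|---|
| Delirium, no psychiatrist or neurologist required, hospitalization not prolonged | AE | Not reported, item (7) | Not serious on this ground |
| Same, hospitalization prolonged | AE | Not reported, item (7) | SAE |
| Delirium requiring one of those specialists | AE | Reported | SAE if a criterion is met |
| Vital-sign abnormality, not life-threatening, hospitalization prolonged | AE | Not recorded, item (1) | SAE |
| Vital-sign abnormality that threatens life | AE | Reported, item (1) | SAE |

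Rows 3 and 5 are consistent. Row 1 conflicts with the AE definition, although an exemption for expected findings could be a deliberate choice. Rows 2 and 4 conflict with both definitions, and nothing settles which prevails. Item (1) also leaves open an event that needs urgent treatment without threatening life: one sentence reports it and the next excludes it.

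**2. Is delirium recorded anywhere else?**

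- It is not a primary or secondary outcome and has no line in the Study Flowchart.
- The list under Symptoms and Physical Examination does not name it. A site could add it, but nothing asks for it.
- The stroke definition includes altered consciousness, but every stroke must be confirmed by imaging. Imaging-negative delirium is outside it.
- ICU stay and ventilation time are collected for everyone. They show a possible consequence, not the event.

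**3. What is not touched**

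Death, RRT, stroke and paraplegia are collected at Visits 3 to 7 whatever the AE rules say. The secondary outcomes come from the bypass and ICU record sheets. No exemption names a spinal event or a focal deficit.

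**4. Illustration**

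Input from Sample Size: 102 patients per arm. Assumptions, because the documents give no rates: true delirium rate d of 10-30%, and recorded share s of 25-75%.

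Unrecorded cases per arm = 102 × d × (1 − s)

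- Low end: 102 × 0.10 × 0.25 = 2.55, about 3
- Half recorded: 102 × 0.10 × 0.50 = 5.1; 102 × 0.20 × 0.50 = 10.2; 102 × 0.30 × 0.50 = 15.3
- High end: 102 × 0.30 × 0.75 = 22.95, about 23

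Recorded rate = d × s

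- Same share in both arms (50%), true rates 30% and 20%: 15% and 10%. The direction is kept and the difference falls from 10 to 5 points.
- No true difference (20% in both arms), shares 40% and 60%: 8% and 12%. A difference appears that does not exist.
- True rates 30% and 20%, shares 40% and 60%: 12% and 12%. A real excess disappears.

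The last two results need recording to differ by arm.

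**The case against.** Exempting expected findings after major aortic surgery is a deliberate and common choice, and item (7) speaks of what symptoms require, which is a test of clinical need rather than of habit. This stands in part. The need is still judged by unblinded staff with no scale or criterion, and the choice does not explain why a serious event has no exception.

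Several stronger readings are tempting, and the documents do not support them.

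- *That the Special Notes remove SAEs.* The SAE definition speaks of any event, not any adverse event, and does not list the Special Notes among its exclusions. A careful site could report an exempted event as an SAE. What the text shows is unstated precedence.
- *That delirium prolonging the ICU stay is automatically an SAE.* The criterion is prolonged hospitalization. A longer ICU stay need not lengthen it.
- *That site habits bias the comparison of arms.* Randomization is done at each centre, so a site's habit falls on all three arms. It loses events and adds noise. Bias needs consulting that differs by arm within sites, which the open-label design permits but nothing demonstrates.
- *That both exemptions depend on consultation.* Only item (7) does. Item (1) rests on the investigator's assessment and keeps the life-threatening events.
- *That CTCAE Grades 1 to 3 oblige recording.* CTCAE grades events already classed as AEs. The capture rule is the AE definition. Grade 3 shows only that an event can be severe without being immediately life-threatening.
- *That spinal protection or transient focal deficits are affected.* Neither is exempted.

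The Statistical Methods section plans no comparison of AEs between arms, so no planned test is distorted. The loss is to the safety record.

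**Conclusion.** The conflict is real and can be read directly from the text. The AE definition, Special Notes items (1) and (7) and the SAE definition give different answers for the same event, and no sentence ranks them. For delirium the threshold is the specialist required rather than severity or seriousness, and no other data item names it. Non-stroke cerebral events can be under-recorded, and unequally by arm if consulting differs by arm.

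The size is unknown. The range of about 3 to 23 unrecorded patients per arm rests wholly on assumed rates of 10-30% delirium and 25-75% unrecorded. A reader might set it against the roughly 13 composite events implied for Group 1 (13% of 102 = 13.3). That comparison would mislead, because delirium is not a component and no composite event is lost. The primary and secondary endpoints stand. This is an inexpensive improvement to the safety record, worth making, and not a threat to the trial's main conclusion.

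**What to change.** 1. Add one sentence to Special Notes: no exemption in this section applies to an event that meets a criterion in Serious Adverse Events.
2. In item (7), replace the specialist condition for delirium with uniform recording: yes/no, start date and stop date, for every patient at Visits 3, 4 and 5, whoever manages it. The dates let Visit 5 pick up episodes that occur between day 3 and discharge.
3. Reconcile item (1) with Definition of Adverse Events and Serious Adverse Events, so that the three sections agree on which vital-sign events are recorded. This includes events that need urgent treatment but are not life-threatening.

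These changes concern recording only and alter no treatment. The cost is protocol wording, one eCRF item, more AE entries per patient and some additional SAE reports.
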